#### 7.3.3 SUSARs

All SAEs assigned by the PI or delegate as both suspected to be related to IMP-treatment and unexpected will be classified as SUSARs and will be subject to expedited reporting to the Regulatory Authority, in the UK: Medicines and Healthcare Products Regulatory Agency (MHRA). The Sponsor (or delegate) will inform the MHRA, and the ethics committee of UK-relevant SUSARs within the required expedited reporting timescales (as per LSHTM Standard Operating Procedure for recording, managing and reporting of adverse events for IMP studies).

For blinded trials, all SUSARs must be reported assuming the active compound is involved.

In the case of a suspected, unexpected, serious adverse reactions (SUSAR), the staff at the site should:

1. Contact the study coordination centre immediately by phone or email to inform them of the event.
2. Submit a completed SAE form (signed and dated) within 24 hours, together with relevant treatment forms and anonymised copies of all relevant investigations.
3. Submit any additional information promptly upon request.

**Contact details for reporting SAEs and SUSARs**  
**[contact] / [name]**  
**Email: [contact]**

## 8. ASSESSMENT AND FOLLOW-UP

### Baseline Data Collection

At baseline (D1) all individuals will undergo a standardized examination to collect data on the presence of skin lesions consistent with yaws, scabies and impetigo. Following examination a finger-prick sample will be obtained from all individuals on to filter paper. In individuals with skin lesions consistent with yaws the same finger prick sample will be used for a rapid diagnostic test for yaws. In individuals with skin lesions consistent with yaws or impetigo two sterile lesion swabs will be obtained.

Following examination individuals will be weighed and directly observed treatment will be dispensed in line with standard treatment guidelines (see above). On D8 study teams will return to each community and offer a second dose of medication for scabies.

### Interim Visit

At Month 3 an interim visit will be made. Individuals will be re-examined and swabs collected from those with clinical evidence of impetigo. Data from previous studies indicates that scabies and impetigo continue to decline between month 3 to month 12 following community mass treatment for scabies therefore treatment will not routinely be offered at this time point.

### Follow-Up Data Collection

At follow-up all individuals will undergo again undergo a standardized examination to collect data on the presence of skin lesions consistent with yaws, scabies and impetigo. Following examination a finger-prick sample will be obtained from all individuals on to filter paper. In individuals with skin lesions consistent with yaws the same finger prick sample will be used for a rapid diagnostic test for yaws. In individuals with skin lesions consistent with yaws the same finger prick sample will be used for a rapid diagnostic test for yaws. In individuals with skin lesions consistent with yaws or impetigo two sterile lesion swabs will be obtained.

In communities where azithromycin mass treatment was not conducted at baseline (sequential treatment arm 2) this will be offered at the follow-up visit.

### Laboratory Work

- Dried blood spots will be eluted at tested using the Treponema Pallidum Haemagglutination Assays.
- From each pair of lesion swabs, one swab will be tested using culture and anti-microbial sensitivity testing for *S. pyogenes* and *S. aureus*.

- The second lesion swab will be tested using molecular techniques to assess the microbiological flora of the lesions.

### **8.1 LOSS TO FOLLOW-UP**

This is not an individually randomised clinical trial but allowance has been made for loss to follow-up in the sample size calculation.

### **8.2 TRIAL CLOSURE**

The trial is planned to run over a 12 month period. The trial will be complete at the end of this 12 month period. SEP

## 9. STATISTICS AND DATA ANALYSIS

### *Sample Size*

The sample size required for our primary outcome was estimated as follows:

- Pre-MDA prevalence of impetigo of 25-30%
- Impetigo prevalence to fall to about 10% in the Ivermectin only arm
- Impetigo prevalence to fall to about 5% in the combined arm
- Enrolment 80%
- Loss to follow-up 10%
- 90% power to detect a difference between the two arms

Primary Outcome:

- a) Prevalence of impetigo at months 12 months in parallel treatment communities compared to sequential treatment communities.

Secondary outcomes:

- b) Change in the proportion of swab samples from which *S. pyogenes* is cultured between baseline and follow-up in the two arms
- c) Proportion of samples from which a drug-resistant isolate is cultured.

Data and all appropriate documentation will be stored for a minimum of 5 years after the completion of the study, including the follow-up period.

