## STUDY SUMMARY

**TITLE** Impact of Single-Dose Azithromycin in Impetigo and Skin Microbiology

**DESIGN** A prospective community intervention trial to assess the impact of community mass treatment with azithromycin for yaws and ivermectin for scabies, on non-yaws bacterial skin infections.

**AIMS** Assess the impact of single dose azithromycin, given for yaws, on other prevalent bacterial skin infections.  
Assess the impact of single dose azithromycin on antimicrobial resistance patterns in isolates of *S.pyogenes* and *S.aureus*.

**OUTCOME MEASURES** Primary Outcome  
a) Difference in the change in prevalence of impetigo between baseline and 12-months between the parallel and the sequential treatment arms.

Secondary Outcomes  
b) Change in the proportion of swab samples from which *S. pyogenes* is cultured between baseline and follow-up in the two arms  
c) The proportion of samples from which a drug-resistant isolate of *S.pyogenes* is cultured in the two arms

**POPULATION** Parallel Treatment Arm: Sample size of 637  
Sequential Treatment Arm: Sample size of 637

**ELIGIBILITY** All residents of selected communities are eligible to participate in the study

**TREATMENT** *Treatment of yaws:*  
Single dose of Azithromycin (30mg/kg, max 2G).

*Treatment of scabies:*

Either an oral dose of Ivermectin (200µg/kg) or permethrin cream for those with a contraindication to Ivermectin (WT<15kg, pregnant or breastfeeding women) given in 2 doses 7-14 days apart.

**DURATION** 12 months

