## **1. INTRODUCTION**

### **1.1 BACKGROUND**

Both trachoma, caused by *Chlamydia trachomatis*, and yaws, caused by *Treponema pallidum* subsp. *pertenue*, are endemic in many Pacific countries including the Solomon Islands[1,2]. Mass treatment with azithromycin is the cornerstone of the WHO strategy for the elimination and eradication of these two diseases respectively[3,4]. Mass treatment with azithromycin has been shown to have beneficial off-target effects including decreased malaria transmission and some evidence to support a reduction in infant mortality [5,6]. Conversely, mass treatment with azithromycin has been associated with changes in the resistance patterns of nasopharyngeal isolates of *Streptococcus pneumoniae*[7].

Scabies is also a significant public health problems in the Pacific[8]. Scabies is associated with secondary bacterial infections (impetigo) which are most commonly caused by *Streptococcus pyogenes* and *Staphylococcus aureus*[9]. Recently community mass treatment with Ivermectin has been shown to be an effective strategy for reducing the prevalence of both scabies and associated bacterial complications[10]. Recent surveys conducted in the Solomon Islands have shown that the prevalence of scabies is between 18-25% and the prevalence of impetigo between 25-40% ([name], personal communication).

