## **3.1 STUDY OUTCOME MEASURES**

### Primary Outcome

a) Difference in the change in prevalence of impetigo between baseline and 12-months between the parallel and the sequential treatment arms.

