## **5. RANDOMISATION AND ENROLMENT PROCEDURE**

### **5.1 RANDOMISATION OR REGISTRATION PRACTICALITIES**

Randomisation will be done at the level of the community by drawing sealed envelopes. All individuals within a community will be offered treatment in line with the randomisation of that community. All residents of the selected communities will be invited to participate in the study.

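### Communities are randomised, but the sample size makes no visible allowance for clustering and no analysis is named, so the stated 90% power is not supported

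*Combined protocol and SAP*

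**What the plan says.** - **Unit of randomisation.** Section 5.1: "Randomisation will be done at the level of the community by drawing sealed envelopes". Everyone in a community is offered that community's allocated treatment. Section 8 (Follow-Up Data Collection) also treats the community as the unit: "In communities where azithromycin mass treatment was not conducted at baseline".
- **Sample-size inputs (Section 9).** Baseline prevalence 25–30%; month-12 prevalence about 10% with ivermectin only and about 5% with the combination; 80% enrolment; 10% loss to follow-up; and "90% power to detect a difference between the two arms". No ICC, between-community variance, design effect, number or size of communities, or alpha is listed.
- **Resulting size (Study Summary).** "Parallel Treatment Arm: Sample size of 637", and the same number in the sequential arm.
- **Allowances (Section 8.1).** "This is not an individually randomised clinical trial but allowance has been made for loss to follow-up in the sample size calculation". Loss to follow-up is the only allowance named there.
- **Primary outcome.** Section 9 gives "Prevalence of impetigo at months 12 months in parallel treatment communities compared to sequential treatment communities". Section 3.1 gives "Difference in the change in prevalence of impetigo between baseline and 12-months between the parallel and the sequential treatment arms".
- **Analysis.** Section 9 lists outcomes but no test, model or interval method. Section 3 (Treatment) refers to site 1 and site 2 without saying how many communities each contains.

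**The concern.** When communities are randomised, people in the same community tend to be more alike than people in different communities. Each extra person from a community already sampled then adds less information than an independent person would. A calculation that ignores this overstates power. An analysis that ignores it gives confidence intervals that are too narrow and a type I error above the nominal level.

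Impetigo is an infectious skin condition, and treatment is given to whole communities. Section 1.1 reports local survey prevalences from 25% to 40%. Identical underlying prevalence in every community is therefore unlikely.

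Two things are at stake: whether the trial has the power it claims, and whether its primary interval will be valid.

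**Working it through.** **Inputs.** From Section 9: p1 = 0.10, p2 = 0.05, power 90%, loss 10%. From the Study Summary: 637 per arm. Alpha is not stated; two-sided 5% is assumed, with one-sided 5% as an alternative. ICC and communities per arm (k) are not stated; the values below are illustrative.

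**1. Reproduce the plan's figure without clustering.**

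Unpooled: n = (1.960 + 1.282)² × (0.10×0.90 + 0.05×0.95) / 0.05² = 577.9 per arm. The pooled-variance form gives 581.1.

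| Allowance for 10% loss | Unpooled | Pooled |
|---|---|---|
| multiply by 1.1 | 636 | 639 |
| divide by 0.9 | 642 | 646 |

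The stated 637 lies among these, and all of them have a design effect of 1.

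**2. Power of 637 with no clustering.** Analysed per arm: 637 × 0.9 = 573.3. SE = √(0.1375/573.3) = 0.01549. Power = Φ(0.05/0.01549 − 1.96) = Φ(1.27) = 89.8%. The loss allowance uses up the whole margin.

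**3. Power with clustering.** Design effect DEFF = 1 + (573.3/k − 1) × ICC; SE = √(0.1375 × DEFF/573.3). Power comes from the noncentral t with 2(k − 1) degrees of freedom, without baseline adjustment. At ICC 0.02, DEFF is 1.55, 2.13 and 3.27 for k = 20, 10 and 5.

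| ICC | k = 20 | k = 10 | k = 5 |
|---|---|---|---|
| 0 | 88% | 86% | 81% |
| 0.01 | 80% | 69% | 49% |
| 0.02 | 71% | 55% | 35% |
| 0.05 | 53% | 35% | 20% |

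The ICC 0 row is below 89.8% only because a community-level t-test has limited degrees of freedom. The rows beneath it add the effect of clustering.

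**4. With baseline adjustment.** Assume a correlation of 0.5 between a community's baseline and month-12 prevalence. Variance of the difference = (0.1375/573.3) × [(1 − ICC) + (573.3/k) × ICC × (1 − 0.5²)], on 2(k − 1) − 1 degrees of freedom.

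| ICC | k = 20 | k = 10 | k = 5 |
|---|---|---|---|
| 0.01 | 82% | 72% | 53% |
| 0.02 | 75% | 61% | 40% |
| 0.05 | 60% | 41% | 23% |

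**5. Alternative readings of 637.**

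- *One-sided 5%, loss only.* n = 473.4 (pooled), so 573.3/473.4 = 1.21 of design effect is available. By normal approximation it is used up at ICC = 0.21/(573.3/k − 1), that is 0.008, 0.004 or 0.002 for k = 20, 10 or 5.
- *One-sided 5%, 80% enrolment and 10% loss.* 471.0/0.72 = 654 to 473.4/0.72 = 658: fairly near 637, again with no design effect.
- *Two-sided 5%, both allowances.* 803 to 807, which does not match 637.
- *637 as residents before enrolment.* 637 × 0.8 × 0.9 = 459 analysed, and power is 82% before any clustering.

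**6. If a person-level test were used** (the plan does not say so). True type I error = 2 × [1 − Φ(1.96/√DEFF)]. At ICC 0.02 this is about 12%, 18% or 28% for k = 20, 10 or 5.

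**The case against.** The strongest reply is that alpha, ICC and number of communities are all unstated, so the size of any shortfall is supplied by assumption. Several parts of that reply stand.

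- **The match to 637 is evidence, not proof.** The two-sided match leaves the listed 80% enrolment unused, and a one-sided level with loss only would leave room for a design effect of 1.21. However, no passage states that reading, and the room disappears at a very small ICC. The other readings that land near 637 contain no design effect.
- **Clustering is not the only penalty.** At two-sided 5%, power is already 89.8% at ICC 0, and with five communities per arm about 9 points are lost to degrees of freedom alone.
- **The survey range is a weak guide to the ICC.** Spreading community prevalence evenly over 25–40% gives SD = 0.15/√12 = 0.0433 and ICC = 0.0433²/(0.325 × 0.675) = 0.0085, hence power of 81%, 71% and 52% for k = 20, 10 and 5. But that range lies between surveys of untreated populations. Carrying the same relative spread (about 13%) to a prevalence of 7.5% gives an ICC of about 0.0014 and power of 87%, 84% and 75%. The loss is then much smaller, but power is still under 90%.
- **Section 3.1 defines a change from baseline,** and adjustment at the person level might recover some precision. The figures above address the month-12 contrast that Section 9 uses.
- **The study-design figure is not visible in the copy reviewed** and may show the number of communities. That would not supply an ICC, an alpha or an analysis method.

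None of these points supplies the missing allowance or the missing analysis.

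**Conclusion.** The concern holds. The plan randomises communities, while its stated inputs and its 637 per arm are consistent with a calculation for independent individuals. At two-sided 5% with 10% loss, 637 gives 89.8% power only if there is no clustering, and less at any positive ICC. The amount lost depends on quantities the plan does not give: from a few points (87% at ICC 0.0014 with 20 communities per arm) to most of the power (35% at ICC 0.02 with five). Only an undocumented one-sided level with no enrolment allowance would leave any room, and that room is small.

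The missing analysis method matters as much as the power. Without it, nothing ensures that the primary comparison reflects variation between communities. If site 1 and site 2 meant one community per arm, that variation could not be estimated at all. This should be corrected before the outcome data are examined.

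**What to change.** In Section 9:

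1. State the planned number of communities per arm, the alpha and its sidedness, and an assumed ICC range with its basis.
2. Replace the single 90% figure with the power that 637 per arm gives over that range.
3. Specify the primary analysis at the level of randomisation. Either a t-test on community summaries or a mixed or GEE model with community as the cluster and a small-sample correction would serve. Adjustment for baseline community prevalence is preferable.
4. Say whether 637 counts people enrolled or residents approached, and how the 80% enrolment figure was used.
5. Clarify that site 1 and site 2 mean the sets of communities randomised to each arm, if that is the intention.
6. State which of the two primary-outcome definitions (Section 3.1 or Section 9) the power and the analysis refer to.

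The cost is wording in Section 9 and a less favourable stated power. The restatement and the community-level analysis need no extra participants. Keeping 90% power at a positive ICC would need more communities or more people; that is a separate choice for the sponsor and is not requested here.

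### The primary outcome has two incompatible definitions (difference in change from baseline, and 12-month prevalence); the stated 637 per arm and 90% power fit the second, and the first has no stated scale

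*Combined protocol and SAP*

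**What the plan says.** The Study Summary and Section 3.1 use the same wording for the primary outcome: "Difference in the change in prevalence of impetigo between baseline and 12-months between the parallel and the sequential treatment arms". Section 9, under its sample size assumptions, gives: "Prevalence of impetigo at months 12 months in parallel treatment communities compared to sequential treatment communities". The first definition uses the baseline survey and the second does not. Both are current text.

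The sample size assumptions in Section 9 are "Pre-MDA prevalence of impetigo of 25-30" per cent, "Impetigo prevalence to fall to about 10% in the Ivermectin only arm", "Impetigo prevalence to fall to about 5% in the combined arm", 80% enrolment, 10% loss to follow-up and "90% power to detect a difference between the two arms". The resulting number appears only in the Study Summary: "Parallel Treatment Arm: Sample size of 637", with the same figure for the sequential arm. Section 5.1 states: "Randomisation will be done at the level of the community by drawing sealed envelopes".

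The documents give no alpha, test, analysis model, scale for the change, correlation between surveys or intra-cluster correlation. The readable text gives no number of communities. The design figure in Section 3 is not shown, so it may hold one.

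**The concern.** An analyst who follows the text can produce two primary results, and the plan does not rank them. The trial is open-label (Section 5.2), so the choice could be made with the data and the allocation in view.

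The two results need not agree. Randomisation gives the absolute difference in change and the 12-month difference the same expected value, but in the trial as run they differ by whatever baseline gap chance leaves between the arms. The scale of the change matters too, because equal falls in percentage points can be unequal falls in relative terms.

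The power statement is also attached to a primary outcome that is not uniquely defined. If it was worked out for one definition, it cannot be assumed to hold for the other.

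**Working it through.** **Inputs.** From Section 9: baseline prevalence p0 = 0.25 to 0.30; 12-month prevalence 0.10 (sequential arm) and 0.05 (parallel arm); 10% loss; 80% enrolment; 90% power. From the Study Summary: 637 per arm. Assumed, because not stated: two-sided alpha 0.05, normal approximation, no design effect. Then (1.960 + 1.282)² = 10.507.

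**1. Rebuilding 637 and 90% from the 12-month comparison.**
- n = 10.507 × (0.10×0.90 + 0.05×0.95) / 0.05² = 10.507 × 0.1375 / 0.0025 = 578 per arm.
- Allowing for 10% loss: 578 × 1.10 = 636, or 578 / 0.90 = 642. The pooled-variance formula gives 582, hence 641 to 647. The plan states 637.
- Analysed per arm: 637 × 0.90 = 573. SE = √(0.1375/573) = 0.0155, and power = Φ(0.05/0.0155 − 1.96) = 89.8%.
- The baseline figure is not used, and neither is the 80% enrolment. Applying enrolment and loss together gives 578/0.72 = 803, or 582/0.72 = 808 (809 rounded up). The match is therefore approximate and treats 637 as the number enrolled. If 637 were counted before enrolment, 637 × 0.8 × 0.9 = 459 would be analysed and 12-month power would be 82%.

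**2. Difference in change, absolute scale.** The expected effect is again 5 points. The variance is the sum over arms of [p0(1−p0) + p1(1−p1) − 2f·p1(1−p0)] / n, where p1 is that arm's 12-month prevalence. Here f = 0 means independent surveys. At f = 1, the maximum possible within-person correlation, every 12-month case was also a baseline case.

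| Baseline | f = 0 | f = 0.5 | f = 1 |
|---|---|---|---|
| 25% | 38.7% | 47.3% | 60.7% |
| 27.5% | 37.3% | 44.9% | 56.4% |
| 30% | 36.1% | 42.8% | 52.8% |

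For example, at 25% and f = 0 the bracketed terms sum to 0.5125, so SE = √(0.5125/573) = 0.0299. Even at f = 1, 90% power needs 1,209 (baseline 25%) to 1,461 (baseline 30%) per arm before loss. So 637 cannot come from this reading.

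**3. Difference in change, ratio scale (delta method, n = 573).**

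| Scale | Change, f = 0 | Change, f = 0.5 | Change, f = 1 | 12-month, same scale |
|---|---|---|---|---|
| Log risk ratio | 81.2-82.7% | 88.0% | 93.0-94.3% | 88.0% |
| Log odds ratio | 78.0-79.1% | 86.1-86.4% | 92.9-94.3% | 88.4% |

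The last column is the fair comparator. For the log risk ratio, SE = √((9 + 19)/573) = 0.221 and the effect is ln 2 = 0.693. The change is less precise than the 12-month comparison at low correlation and more precise at high correlation. On the log risk ratio the change reaches 90% at f = 0.65 to 0.69, so it too can be made to give about 637, but only with a correlation that the documents do not state.

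**4. How far the two results can part.** Hold 12-month prevalence at 10% (sequential) and 5% (parallel), a difference of 5 points.
- Baseline 30% sequential, 25% parallel: falls of 20 and 20 points, difference in change 0. The relative falls are 67% and 80%.
- Baseline 25% sequential, 30% parallel: falls of 15 and 25 points, difference in change 10.

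The 25-30% in Section 9 is uncertainty about one prevalence, not an expected gap between arms; these cases are illustrations. Without clustering, the SE of the baseline gap is √(2p0(1−p0)/637) = 0.0243 to 0.0257, so a gap of 5 points or more in either direction has a chance of about 4-5%. At assumed design effects of 2 and 5 it is about 15-17% and 36-38%.

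**The case against.** The strongest reply is that the Section 9 wording is loose shorthand: its assumptions are framed as falls from a stated baseline, its outcome list is abbreviated elsewhere too, and under randomisation both definitions have the same expected absolute difference. That is plausible as an account of how the text arose. It does not say which result is primary, and equal expectation does not prevent different realised answers.

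Three stronger conclusions that a reader might infer are not supported.
- That 637 can come from the 12-month comparison and nothing else. A log-risk-ratio change also reaches about that number with a suitable correlation. What stands is that the 12-month comparison is the only reading that gives 637 without assuming a within-person correlation absent from the documents. It still needs an assumed alpha and sets aside the listed enrolment figure.
- That the difference in change is underpowered on every scale. On a ratio scale it brackets the 12-month comparison, so no clear loss is shown.
- That adjusting for baseline costs nothing in power. That is a large-sample, individual-level result. Communities are randomised, and Section 3 speaks of a site 1 and a site 2; with few communities, community-level adjustment uses scarce degrees of freedom or may not be possible.

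Clustering also limits the ranking. A change score removes stable differences between communities, so with strong community correlation over time it could be the more precise choice. The imbalance chances above 5% rest on assumed design effects.

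**Conclusion.** The contradiction stands and must be resolved before analysis: two current definitions of the primary outcome, no rule to choose between them, and no scale for one of them. The stated 637 and 90% are approximately those of 10% v 5% at 12 months with 10% loss. They do not hold for an absolute difference in change, whose power is 36-61% across the whole range of within-person correlation. For a ratio-scale change, power is 78-94% depending on that unstated correlation, and no deficit relative to the 12-month comparison is established.

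All of this assumes two-sided alpha 0.05, 573 analysed per arm and no clustering. The figures compare the definitions under those assumptions. They are not the trial's true power, and allowing for randomisation by community could change the ranking.

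**What to change.** State one primary outcome, in identical words and with its scale, in the Study Summary, Section 3.1 and Section 9. That alone removes the contradiction.

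A suitable choice is 12-month impetigo prevalence compared between arms, adjusted for the baseline impetigo already recorded on D1 as far as the number of communities allows, in an analysis that respects randomisation by community. The difference in change would be supportive. If the difference in change is kept as primary, state its scale and the assumed correlation between surveys, and restate the power for it.

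The cost is wording in three places and a restated power figure, which needs an assumed intra-cluster correlation and the number of communities. The amendment may need a favourable opinion from both ethics committees (Section 11.1). Community-level adjustment would cost some degrees of freedom. No new data are needed.
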